4.3.4 Replacement Policy

It is planned to randomize approximately 400 patients. Discontinued patients in this study will not be replaced.

Verona Pharma plc CONFIDENTIAL Page 30 of 67

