5.7 Method of Assigning Patients to Treatment Groups

All patients consented will be assigned a patient identification (PID) number upon signing of the informed consent using the following convention: XXX-YYY where XXX is the center number and YYY is the patient number (001, 002, etc.). Patients will receive one of the five different treatment options in the study (see Section 5.1). Patients will be equally randomized to one of the four doses or placebo before the first study medication administration at Visit 2. Medication identification numbers will be provided on the study medication kit.

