7.1.3 Reversibility Test

Reversibility in response to albuterol/salbutamol will be assessed at screening (Visit 1) as an eligibility measure. Spirometry (FEV₁ and FVC) assessment before and after four puffs of albuterol/salbutamol are administered using a pMDI will be performed.

At both time points, three technically acceptable and reproducible measurements should be made in accordance with the requirements described in Section 7.2.1. The highest reading from each assessment will be used for calculation of predicted values and increase from baseline.

The following must be confirmed post-albuterol/salbutamol dose for inclusion:

- Post-bronchodilator FEV₁/FVC ratio of <0.70
- Post-bronchodilator FEV₁ ≥40 % and ≤80% of predicted normal*
- *National Health and Nutrition Examination Survey (NHANES) III (Hankinson et al., 1999) will be used as a reference for normal predicted values.

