3.3. Determination of Sample Size

The standard deviation for peak FEV1 is estimated to be 250 mL. With a 2-sided test at a 5% significance level and 80 evaluable patients per group, there will be an 80% power to detect a true difference of 111 mL between any two treatments. This detectable limit has been considered sufficient to conclusively identify a minimal effective dose of RPL554. Thus 80 patients per group will be randomized for a total of 400 patients.

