5.6.2. Analysis of Primary Endpoint

The primary efficacy analysis parameter is change from baseline FEV₁ to peak FEV₁ at Week 4 of treatment. The primary analysis will be based on the full analysis set.

Summary statistics for FEV₁ will be presented for baseline, week 4 and change from baseline by treatment group on patients with both assessments.

The primary analysis will use a restricted maximum likelihood (REML)–based repeated-measures approach. The change from baseline FEV₁ (at Day 1, Week 1, 2 3 and 4) will be the dependent variable. The analyses will include the fixed, categorical effects of treatment, visit, and treatment-by-visit interaction as well as the continuous, fixed covariates of baseline value. An unstructured (co)variance structure shared across treatment groups will be used to model the within-patient errors. If the model does not converge a compound symmetry (co)variance structure will be used. The Kenward-Roger approximation will be used to estimate denominator degrees of freedom and adjust standard errors. Analyses will be implemented with SAS PROC MIXED (see Appendix 4: SAS code for efficacy analysis). The primary comparison will be the contrast (difference in least squares mean [LSMEAN]) between treatments at Week 4.

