9.4. Appendix 4: SAS code for efficacy analysis

```
proc mixed data=efficacy;
class subject trt country visit;
model outcome= trt visit trt*visit b_fev /ddfm=kr;
repeated visit/ sub=subject type=un;
lsmeans trt*visit/ cl diff;
```

run;

where outcome is the change from baseline

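### The primary model omits screening FEV1 reversibility, a pre-randomization covariate already collected; adding it costs little, but the size of the gain is an assumption

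*SAP*

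**What the plan says.** Protocol 7.1.3 states: "Reversibility in response to albuterol/salbutamol will be assessed at screening (Visit 1) as an eligibility measure". FEV1 is read before and after four puffs, so a change in mL exists for each patient before randomization. Eligibility bounds the post-bronchodilator FEV1 and the FEV1/FVC ratio but sets no minimum reversibility (Protocol 4.1, criterion 8).

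SAP 4.2 lists reversibility among the baseline characteristics, to be summarized without testing. It has no other role. It is absent from the sensitivity analyses (SAP 5.6.2.1) and the subgroups (SAP 5.6.6). SAP 5.6.2 describes the primary model as treatment, visit and their interaction, "as well as the continuous, fixed covariates of baseline value". The Appendix 4 code agrees on covariates: "model outcome= trt visit trt*visit b_fev /ddfm=kr". The ANCOVA in Protocol 9.2.2.5 likewise has pre-dose FEV1 as its only continuous covariate. No reason is given for leaving reversibility out.

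On precision, SAP 3.3 states: "The standard deviation for peak FEV1 is estimated to be 250 mL". Its calculation assumes two-sided testing at 5% and groups of 80 evaluable patients, and its conclusion is that "there will be an 80% power to detect a true difference of 111 mL between any two treatments".

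**The concern.** The primary endpoint is the rise from pre-dose FEV1 at Visit 2 to the highest reading within 3 hours of inhaling study drug. Screening reversibility is the same kind of quantity, a rise in FEV1 after an inhaled bronchodilator. Pre-dose FEV1 measures level, not capacity to bronchodilate. If capacity varies between patients and carries over to the endpoint, that variation stays in the error term although a measure of it is on file.

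Precision matters here for two reasons. The sample size has no margin: 80 evaluable patients per group are needed and 80 are randomized, and "Discontinued patients in this study will not be replaced". In addition, SAP 5.6.4 tests doses in a fixed sequence from 6 mg down and stops at the first failure, so the lower doses, which bear on the minimal effective dose, are reached only if every earlier test succeeds.

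**Working it through.** **Inputs.** SD 250 mL, difference 111 mL, 80 per group, two-sided 5% (SAP 3.3). Equal allocation: "Patients will be equally randomized to one of the four doses or placebo" (Protocol 5.7). The partial correlation r of reversibility with the endpoint, given baseline FEV1, is not in the documents. It is assumed to be 0 to 0.4.

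**1. The plan's own figure.** SE = 250 × √(2/80) = 39.53 mL. Detectable difference at 80% power = 39.53 × (1.960 + 0.842) = 110.7 mL. Power at 111 mL is 80.2% (normal), 79.7% (t, 158 df) or 80.0% (t, pooled 395 df). The stated 111 mL and 80% reproduce.

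**2. Same slope in every arm.** Residual SD = 250 × √(1 − r²), taking 250 mL as the residual SD before the new term. The term uses about 1 of roughly 395 df.

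| Assumed r | Variance removed | Residual SD (mL) | Detectable (mL) | Power at 111 mL, normal | Power, t (394 df) | n per group for 80% |
|---|---|---|---|---|---|---|
| 0 | 0% | 250.0 | 110.7 | 80.2% | 80.0% | 80 |
| 0.1 | 1% | 248.7 | 110.2 | 80.6% | 80.4% | 79 |
| 0.2 | 4% | 244.9 | 108.5 | 81.8% | 81.6% | 77 |
| 0.3 | 9% | 238.5 | 105.6 | 83.7% | 83.6% | 73 |
| 0.4 | 16% | 229.1 | 101.5 | 86.5% | 86.4% | 67 |

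A t calculation on two arms alone gives 81.3%, 83.3% and 86.1% for r of 0.2, 0.3 and 0.4, hence the rounded ranges used here.

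**3. Reversibility predicts response only on active drug.** As an extreme case, let the covariate have variance 1, slope b in the four active arms and slope 0 on placebo, with remaining variance σ².

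- A single main effect estimates the average slope over five equal arms, 0.8b.
- Contrast variance × n without the term: (σ² + b²) + σ² = 2σ² + b².
- With the term: (σ² + 0.04b²) + (σ² + 0.64b²) = 2σ² + 0.68b².
- Pooled residual variance with the term: σ² + (4 × 0.04 + 0.64)b²/5 = σ² + 0.16b². The model reports twice this for the contrast.
- Scale the pooled variance without the term to 1, so σ² + 0.8b² = 1. The pooled variance removed is then r² = 0.64b².

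| Pooled r | b² | σ² | True, without term | True, with term | Fall | Model-based, with term | Shortfall |
|---|---|---|---|---|---|---|---|
| 0.2 | 0.0625 | 0.95 | 1.9625 | 1.9425 | 1.0% | 1.92 | 1.2% |
| 0.3 | 0.1406 | 0.8875 | 1.9156 | 1.8706 | 2.3% | 1.82 | 2.7% |
| 0.4 | 0.25 | 0.80 | 1.85 | 1.77 | 4.3% | 1.68 | 5.1% |

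The true contrast variance falls by 1.0%, 2.3% or 4.3%, against the 4%, 9% or 16% of step 2. The placebo arm is adjusted with a slope it does not have. Because SAP 5.6.2 uses one covariance matrix for all arms, the reported variance is then about 1-5% too small.

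**The case against.** The strongest reply is that this is a preference. Nothing in the protocol or SAP promises a reversibility covariate, its two stated uses (eligibility and baseline description) are both honored, and randomization keeps the planned contrast unbiased. All of that stands, and it is why the point is a suggested improvement.

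The second reply is that the benefit is assumed. This also stands. Protocol 1.1 reports that RPL554 alone performed similarly to standard bronchodilators, but that is a group-level comparison from a crossover study and gives no within-patient correlation. The SAP does not say whether 250 mL refers to change from baseline or to a baseline-adjusted residual. The rationale itself, capacity to bronchodilate, points toward a slope on active drug and less on placebo, which is the less favorable case in step 3.

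A reader might infer that the plan gives up free precision worth as many as 95 patients per group. That figure is 80/(1 − 0.16) = 95.2. It needs r = 0.4, a common slope in all arms and 250 mL as the residual SD. The documents support none of the three.

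The practical objections carry less weight. SAP 3.8.1 allows no further imputation, and PROC MIXED drops records with a missing covariate, so a patient without a usable value would leave the analysis. Eligibility requires this spirometry, however, so such cases should be rare. The reading may be noisy: Protocol 3.1 places the washout instruction after screening while Protocol 5.9.1 requires withholding before Visit 1, and those passages must be reconciled. Noise would reduce the gain but would not bias the treatment comparison. The absence of country from the MODEL statement is a separate matter.

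**Conclusion.** The point holds as a low-severity missed opportunity. A pre-randomization measure, available on all patients and plausibly related to the primary endpoint, is left out of the model without a stated reason.

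The gain cannot be read from the documents. It runs from nothing at r = 0, through about half a power point at r = 0.1, to about 6 points at r = 0.4 under a common slope. It is much smaller if reversibility matters only on active drug. A reader might also infer that the planned analysis is biased or the trial underpowered for want of this term. Neither follows: the analysis is valid as written and the sample size reproduces without it.

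**What to change.** In SAP 5.6.2 and Appendix 4, add the screening change in FEV1 after albuterol/salbutamol (mL) as a continuous fixed covariate in the MMRM for the FEV1 endpoints. Specify it before unblinding and log it in SAP 3.4 as a change from the protocol model. State in SAP 3.8.1 how a patient without a usable value is handled. SAP version 1.0 describes itself as final and for use after database lock, and Protocol 5.8 holds the blind until lock. If the blind has already been broken, leave the primary model unchanged and run the adjusted model only as a labelled sensitivity analysis.

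The cost is one model term, about one degree of freedom, and any patient lost to a missing reversibility value. No new data are needed. Any report of the expected benefit should present the power figures as assumptions.

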5.6.3. Analyses of Secondary and exploratory Endpoints

The secondary and exploratory endpoints will be analyzed in the same way as the primary endpoint.

In the analysis of TDI, BDI scores will be used as baseline in the model and the dependent endpoint will be the TDI score.

As for PGAC the model will not include the baseline as the score reflect itself a change from baseline.

The number of COPD exacerbations and use of rescue medications will be summarized by counts and percentages.

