5.6.6. Examination of Subgroups

The following subgroups will be examined:

1. Current vs. ex-smokers
2. Chronic bronchitis vs. no chronic bronchitis at screening
3. Males vs. females.
4. Symptoms severity (MRC <2 vs. MRC \geq 2) at randomization
5. Age: (\geq 65 vs < 65)
6. Inhaled corticosteroid use versus no use (use of medications during the last 7 days of run-in phase).
7. By baseline FEV1 (> or \leq 50% predicted)

Subgroup analyses will be performed for the primary and the selected secondary endpoints (see 5.4).

The MMRM model will be run on each subgroup separately.

6. Safety Endpoints

Safety measures that will be collected and investigated include adverse events (AEs), clinical

laboratory tests, vital signs, physical examination and electrocardiograms assessments (ECGs, 12-Lead and using 24 hour Holter monitors).

All safety analyses will be performed on the safety analysis set. Patients will be analyzed according to the treatment received. All safety summaries will present the five treatment groups.

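### If the unstructured model fails, SAP 5.6.2 falls back directly to compound symmetry, which can misstate the Week 4 standard error in either direction; heterogeneous structures should be tried first

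*SAP*

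**What the plan says.** SAP 5.6.2 models change from baseline FEV₁ at five visits (Day 1 and Weeks 1 to 4). The covariance is unstructured and shared across arms, and Kenward-Roger is used for standard errors and degrees of freedom. The primary comparison is the Week 4 difference in least squares means. The only provision for a failed fit is one sentence: "If the model does not converge a compound symmetry (co)variance structure will be used". No intermediate structure, change of algorithm or robust standard error is named, and the code in SAP Appendix 4 contains only the unstructured model.

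The rule reaches beyond the primary endpoint. SAP 5.6.3 states "The secondary and exploratory endpoints will be analyzed in the same way as the primary endpoint", and SAP 5.6.6 states "The MMRM model will be run on each subgroup separately". Section 5.6.6 lists seven two-level factors, which makes 14 separate models per endpoint.

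The only variance figure in either document is a single one: "The standard deviation for peak FEV1 is estimated to be 250 mL" (SAP 3.3; the same value is in Protocol 9.3). It is not broken down by visit, and no between-visit correlation is given.

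**The concern.** Compound symmetry assumes equal variance at every visit and equal correlation between every pair of visits. The test is made at one visit, but the variance it uses would be pooled over all five.

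The design gives a reason to doubt equal variance. SAP 5.1 takes baseline 15 minutes before dosing at Visit 2, the same morning as the Day 1 peak. The later peaks are one to four weeks away from baseline. The Day 1 change therefore plausibly carries less day-to-day variation than the changes at Weeks 1 to 4. If so, pooling pulls the Week 4 variance down and the Week 4 test rejects too often.

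Kenward-Roger adjusts for small samples within the assumed structure and does not repair a wrong one. The fixed-sequence procedure in SAP 5.6.4 takes its p-values from this model, so its claim of strong family-wise control depends on the standard error being right. If the fallback were used, confidence intervals would also have the wrong width.

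**Working it through.** **The plan's own figure.** Inputs from SAP 3.3 are SD 250 mL, two-sided 5%, 80 per group and 111 mL: "there will be an 80% power to detect a true difference of 111 mL between any two treatments". Allocation is equal across five arms (Protocol 5.7).

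- SE of a two-arm difference = 250 × √(2/80) = 39.5 mL.
- Detectable difference = (1.960 + 0.842) × 39.5 = 110.7 mL (111.4 mL with the t distribution).
- Power at 111 mL is 80.2% (normal) or 79.7% (t).

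The stated sample size reproduces and is not affected by this point.

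**Effect of compound symmetry with complete data.**

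- Ratio r = reported SE / true SE at Week 4 = √(mean of the five visit variances / Week 4 variance).
- Actual two-sided type I error = 2 × (1 − Φ(1.96 × r)).

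The SDs below are residual SDs by visit. They are **assumptions**, because the documents give none.

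| Assumed SD, Day 1 / Weeks 1, 2, 3, 4 (mL) | Mean variance / Week 4 variance | r | Type I error |
|---|---|---|---|
| 250 at all visits | 62,500 / 62,500 | 1.000 | 5.0% |
| *Only Day 1 smaller* | | | |
| 200 / 250 throughout | 58,000 / 62,500 | 0.963 | 5.9% |
| 200 / 260 throughout | 62,080 / 67,600 | 0.958 | 6.0% |
| 180 / 250 throughout | 56,480 / 62,500 | 0.951 | 6.2% |
| 180 / 260 throughout | 60,560 / 67,600 | 0.946 | 6.4% |
| *Variance also rising to Week 4* | | | |
| 200 / 240, 250, 250, 260 | 58,040 / 67,600 | 0.927 | 6.9% |
| 180 / 230, 240, 250, 260 | 54,600 / 67,600 | 0.899 | 7.8% |
| *Other patterns* | | | |
| 300 / 250 throughout | 68,000 / 62,500 | 1.043 | 4.1% |
| 300 / 287.5, 275, 262.5, 250 | 75,937.5 / 62,500 | 1.102 | 3.1% |
| 200 / 270, 280, 270, 250 | 65,340 / 62,500 | 1.022 | 4.5% |

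If only Day 1 differs, there is a ceiling. With zero Day 1 variance, r = √(4/5) = 0.894 and the type I error is 8.0%.

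**Check with dropout.** Compound symmetry fitted by REML was simulated under the null: 5 arms of 80, five visits, a baseline covariate and 10% dropout completely at random. The documents state no dropout rate, so the 10% is an assumption; Protocol 4.3.4 says only "Discontinued patients in this study will not be replaced". There were 8,000 runs per scenario, and Monte Carlo error is about 0.25 percentage points.

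- Equal SDs: 4.5% with exchangeable correlation 0.7, 5.3% with AR(1) correlation 0.85.
- Day 1 SD 200 against 250 mL: 6.1%.
- Steady rise from 200 to 250 mL: 8.2%.
- Day 1 SD 300 against 250 mL: 4.1%.
- Steady fall from 300 to 250 mL: 3.5%.

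With the true covariance standing in for a converged unstructured fit, the range was 4.6% to 5.3%.

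**Where the rule could be triggered.** Five visits need 5 × 6 / 2 = 15 unstructured parameters, set against about 400 patients. By SAP 5.2, peak and 3-hour average FEV₁ have five visits including Day 1. Trough FEV₁ has Weeks 1 to 4 only. The 12-hour average has two visits, so only 3 parameters. The symptom scores have no Day 1 change.

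**The case against.** The strongest objection is that no inflation has been shown. A reader might infer from the same-morning baseline that Day 1 variance is certainly smaller and that the fallback therefore does inflate the type I error. The documents do not support that. They give one SD of 250 mL and nothing by visit. The direction depends on the whole pattern: compound symmetry is conservative if variance falls to Week 4, and also with a mid-study peak even when Day 1 is smaller (4.5% above). This part of the objection stands, and the point has to be conditional.

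Second, the same-morning argument explains a lower Day 1 but not a further rise from Week 1 to Week 4. This also stands. The figures of 7% to 8% need that extra assumption; the Day 1 mechanism alone gives about 6%.

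Third, the trigger is remote where it would matter most. Failure of the primary model is unlikely at this size, and the LOCF ANCOVA in SAP 5.6.2.1 does not use compound symmetry, although it is only a sensitivity analysis. Failure is easier to imagine in small strata, for example MRC below 2, which is grade 1 only, split over five arms. Neither document gives stratum sizes, however, and none of those analyses claims error control: SAP 5.6.5 confines it to the primary endpoint.

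Fourth, an obvious remedy can do harm. In a simulation with complete null data, SDs 180/250/250/250/250 mL and correlation 0.7, uncorrected sandwich standard errors gave a Week 4 type I error of 10.3% at 5 per arm, against 6.7% for model-based compound symmetry. At 10 per arm the figures were 7.7% and 6.9%. This stands and limits the fix.

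None of this defends compound symmetry as the first fallback. Unless the Week 4 variance happens to equal the five-visit average, it gives the wrong Week 4 standard error.

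**Conclusion.** The point holds as a conditional weakness in a pre-specified rule. If the fallback is used, the Week 4 standard error is wrong by the factor r, and Kenward-Roger does not correct it. On the assumption that only Day 1 is less variable (180 to 200 mL against 250 to 260 mL), the type I error is about 6% (5.9% to 6.4%). It is about 7% to 8% if variance also rises through Week 4, 5% with equal variances, and roughly 3% to 4% with lost power if variance falls to Week 4.

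The Day 1 argument concerns endpoints with a Day 1 value, in practice peak and 3-hour average FEV₁. The 12-hour average also has one, but with two visits its unstructured model should converge. The argument does not extend to trough FEV₁ or the symptom scores.

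A reader might conclude that the primary result or the sample size is compromised. Neither follows: the sample size reproduces, and the primary model will probably converge as unstructured. This is a cheap improvement to the plan, not a demonstrated error-rate problem.

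**What to change.** Replace the fallback sentence in SAP 5.6.2 with a fixed sequence and use the first structure that converges:

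1. unstructured;
2. unstructured with Fisher scoring and supplied starting values;
3. heterogeneous Toeplitz;
4. heterogeneous AR(1);
5. heterogeneous compound symmetry;
6. homogeneous compound symmetry, only as a last resort.

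Steps 3 to 5 keep a separate variance for each visit, which is what the Week 4 contrast needs. State that the sequence also applies to the models in SAP 5.6.3 and 5.6.6, and report which structure was used.

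Do not require uncorrected sandwich standard errors. If a robust standard error is wanted, name a small-sample-corrected version and its degrees of freedom, and do not use it in small subgroups.

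The cost is one or two sentences in the SAP and slightly more programming. Results do not change if the unstructured model converges, and no covariance structure has to be chosen after unblinding.

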5.6.2.1. Sensitivity analysis for the primary endpoint

To check the robustness of the results the following analysis will be performed:

- MMRM analysis excluding the patients with only one on treatment assessment of peak FEV₁ (over 3 hours)
- analysis of covariance (ANCOVA) will be used on data where missing data will be imputed using last observation carried forward (LOCF) method.

5.6.3. Analyses of Secondary and exploratory Endpoints

The secondary and exploratory endpoints will be analyzed in the same way as the primary endpoint.

In the analysis of TDI, BDI scores will be used as baseline in the model and the dependent endpoint will be the TDI score.

As for PGAC the model will not include the baseline as the score reflect itself a change from baseline.

The number of COPD exacerbations and use of rescue medications will be summarized by counts and percentages.

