6.3.1 Pre-Dose Assessments

The following assessments will be performed prior to dosing:

- Confirmation that respiratory medication and other restrictions described in Section 5.9.1 and Section 6.1, respectively, were properly followed. If not, reschedule the visit for within the required window
- Collection of demographic variables (date of birth, sex, height, weight, race and smoking status)
- Questioning for adverse events
- Concomitant medication check
- Review of e-diary to confirm compliance with the device
- Urine pregnancy test (female patients of childbearing potential)
- 12-lead ECG
- Vital signs (blood pressure and pulse rate)
- Patients will complete the SGRQ-C, BDI and MRC breathlessness scale
- Spirometry at 15 minutes pre-dose; must demonstrate that the FEV₁ be within 20% of the pre-albuterol/salbutamol FEV₁ recorded at Visit 1

Patients who remain eligible will then be randomized and assigned a randomization number.

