7.2.5 Patient Global Assessment of Change

At Visits 4 and 6, patients will be asked to respond to a PGAC question asking, "Compared with prior to the study start, how do you feel your breathing is?" on a scale of '1=much worse' to '5=much better', with '3=no change'.

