Average EXACT-PRO total scores, average daily use of rescue medication, SGRQ-C total scores, MRC, global assessment of change, and TDI scores will be compared between the five treatments using ANCOVA models with treatment and country(/center) as factors and using baseline as a covariate where appropriate. Subdomain scores of the EXACT-PRO and SGRQC will be summarized and subjected to exploratory analyses.

The number of COPD exacerbations will be summarized by treatment group.

Testing for efficacy will start with the highest dose of RPL554 versus placebo. If a statistically significant difference is found, the testing will proceed with the next highest dose, and so on. Secondarily, the various doses of RPL554 will be compared. Appropriate measures will be taken to control for the type I error rate in these hypothesis tests. A closed testing procedure to test active dose vs. placebo will be used for the primary endpoint. The study is not powered for pairwise differences between active doses. Thus, dose-response is best investigated in a secondary analysis fitting an appropriate dose-response model to the data. The Statistical Analysis Plan will provide additional details of the multiplicity adjustment method(s) used.

All hypothesis testing will be done using two-sided alternative hypotheses. P-values less than 5% will be considered statistically significant.

9.2.2.6 *Safety*

Safety data, including safety laboratory tests, ECG parameters, Holter monitors, vital signs and physical examinations, will be summarized by treatment group and time point, when appropriate. For continuous variables, the change from baseline (both regarding pre-dose at Visit 2 and pre-dose at each treatment visit) to each post-dose time point will also be calculated and summarized. Data will further be illustrated by shift tables (showing changes from low/normal/high) and shift plots for selected time points.

Coded adverse event terms will be presented by system organ class (SOC) and preferred term and summarized by treatment group. A summary table by treatment group with total number and number of patients with adverse events, SAEs, adverse events leading to discontinuation of study medication, causally related adverse events and severe adverse events will be produced. Further SAEs, causally related adverse events and adverse event of each intensity will be summarized by SOC and preferred term.

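### The PGAC model has no baseline covariate because PGAC is itself a change score; that reason does not rule out adjusting for BDI, and some precision may be lost on an exploratory endpoint

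*SAP*

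**What the plan says.** SAP 5.6.3 analyses the secondary and exploratory endpoints like the primary one, that is, with the mixed model of SAP 5.6.2. Besides treatment, visit and their interaction, that model has one baseline term: "as well as the continuous, fixed covariates of baseline value". The code in SAP Appendix 4 shows it as baseline FEV1: "model outcome= trt visit trt*visit b_fev /ddfm=kr".

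SAP 5.6.3 then makes two exceptions, in adjacent sentences:

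- TDI: "In the analysis of TDI, BDI scores will be used as baseline in the model and the dependent endpoint will be the TDI score".
- PGAC: "As for PGAC the model will not include the baseline as the score reflect itself a change from baseline".

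Protocol 9.2.2.5 names global assessment of change among the endpoints to be compared by "ANCOVA models with treatment and country(/center) as factors and using baseline as a covariate where appropriate".

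On timing, Protocol 7.2.5 says: "At Visits 4 and 6, patients will be asked to respond to a PGAC question asking". SAP 5.5.5 and the schedule of assessments agree. The protocol synopsis can be read as placing the question at Visit 2 as well, but the detailed sections do not. BDI is taken at Visit 2 before dosing and before randomization, with two other possible covariates (Protocol 6.3.1): "Patients will complete the SGRQ-C, BDI and MRC breathlessness scale".

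**The concern.** The stated reason is that a score which already expresses change needs no baseline. But a change can still depend on where the patient started, and a baseline covariate removes the part of the outcome variance that starting status explains. The SAP relies on this elsewhere: its primary endpoint is a change in FEV1 adjusted for baseline FEV1. In the sentence just before the PGAC one, it adjusts TDI for BDI, although TDI is a transition score with no earlier TDI value. The reason given for PGAC would apply equally to TDI.

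PGAC asks how breathing compares with the time before the study. Breathlessness at that time is measured at Visit 2 by BDI and MRC grade. If it predicts the PGAC answer, an unadjusted model leaves that variance in the error term, and the four dose-versus-placebo contrasts are less precise than the collected data allow.

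**Working it through.** **1. The plan's own figure.** The only power statement (Protocol 9.3, SAP 3.3) concerns peak FEV1: SD 250 mL, difference 111 mL, two-sided 5%, 80 evaluable patients per group, 80% power.

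- n per group = 2 × (1.960 + 0.842)² × (250/111)² = 79.6, rounded up to 80.
- Standardized difference = 111/250 = 0.444. The standard error of a difference in SD units is √(2/80) = 0.158. Power = Φ(0.444/0.158 − 1.960) = 80.2% (79.7% with the noncentral t).

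The stated figure reproduces. There is no such statement for PGAC.

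**2. What a covariate would add.** A baseline covariate with correlation ρ to the outcome multiplies the residual variance by (1 − ρ²) and the standard error by √(1 − ρ²). The documents give no PGAC SD, no PGAC effect size and no PGAC–BDI correlation. Both ρ (taken as an absolute value) and the 0.444 SD effect borrowed from FEV1 are therefore assumptions. With 80 per arm, power is Φ(0.444/(0.158 × √(1 − ρ²)) − 1.960), and the equivalent unadjusted n is 80/(1 − ρ²):

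| Assumed ρ | Variance reduction | SE ratio | Equivalent unadjusted n per arm | Power at 0.444 SD |
|---|---|---|---|---|
| 0 | 0% | 1.000 | 80.0 | 80.2% |
| 0.1 | 1% | 0.995 | 80.8 | 80.6% |
| 0.2 | 4% | 0.980 | 83.3 | 81.8% |
| 0.3 | 9% | 0.954 | 87.9 | 83.7% |
| 0.4 | 16% | 0.917 | 95.2 | 86.5% |
| 0.5 | 25% | 0.866 | 106.7 | 90.0% |

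The variance column depends only on ρ. The power column also needs the borrowed effect size and is for illustration.

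**3. Bias or precision?** A five-category score was simulated by cutting a normal variable with a 0.444 SD treatment shift (two arms of 80, 3,000 runs per ρ, with ρ set before cutting). It was analysed with and without the baseline covariate:

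| ρ | Mean effect, unadjusted | Mean effect, adjusted | SE ratio |
|---|---|---|---|
| 0 | 0.425 | 0.425 | 1.005 |
| 0.1 | 0.420 | 0.419 | 1.000 |
| 0.3 | 0.429 | 0.429 | 0.962 |
| 0.5 | 0.430 | 0.430 | 0.870 |

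The mean effects agree within 0.001. Only the precision differs, and at ρ of 0 or 0.1 there is nothing to gain.

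**4. Chance imbalance in a single trial.** A two-standard-error difference in baseline between two arms is 2 × 0.158 = 0.316 SD. At an assumed ρ of 0.3 it moves the unadjusted contrast by 0.3 × 0.316 = 0.095 SD. The unadjusted standard error already allows for this on average; adjustment corrects for the imbalance that actually occurs.

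**The case against.** The strongest reply is that nothing usable was left out. The parent model's one baseline term is the endpoint's own baseline, and PGAC has none because it is asked only at Visits 4 and 6. BDI and TDI are paired instruments with matching domains, and Protocol 7.2.6 defines TDI as change from the state that BDI measures, so BDI is TDI's natural baseline in a way that it is not for PGAC. The protocol requires adjustment only by "using baseline as a covariate where appropriate". SAP 5.6.5 treats secondary endpoints as exploratory, and PGAC is not among the selected endpoints of SAP 5.4. The gain rests on an unknown correlation, and MRC or SGRQ-C could serve in place of BDI.

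All of this stands as to status and size. It explains why the two scores were handled differently, but it does not rescue the reason the SAP gives: a covariate need not be an earlier value of the same score to be valid or useful.

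A reader might infer more than the documents support:

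- *That the PGAC contrast is biased or its type I error inflated.* Under randomization it is neither, and at ρ = 0 baseline imbalance has no influence.
- *That the SAP contradicts the protocol.* The protocol's wording permits the omission.
- *That PGAC and TDI can no longer be read together.* In a linear model the covariate does not alter the mean difference being estimated, and the two scores are on different scales in any case (1 to 5, and −9 to 9).

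**Conclusion.** The point holds as a missed, optional gain in precision. The SAP's reason for fitting PGAC without a baseline covariate is not sound, and a suitable pre-randomization measure is already collected. The residual variance reduction given up is 1% to 25% if the PGAC–BDI correlation is between 0.1 and 0.5. The documents do not show where in that range it lies, or that it lies there at all; at zero the gain is nil. No primary conclusion depends on it.

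**What to change.** In SAP 5.6.3, replace the PGAC sentence with: *In the analysis of PGAC, the BDI total score at Visit 2 will be included as the baseline covariate, as for TDI.* In the Appendix 4 code this term takes the place of the baseline FEV1 term; the rest of the mixed model stays unchanged. BDI is preferred to MRC or SGRQ-C because it puts PGAC on the same footing as TDI; what matters most is that one covariate is fixed in advance.

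The cost is one sentence, one model term and one degree of freedom in about 400 patients, with no new data. Any patient without a Visit 2 BDI would drop out of the PGAC model, as already happens for TDI; the current PGAC model keeps such patients.

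The SAP's modification history labels this version for use after database lock. If treatment codes are already open, keep the unadjusted model as planned and report the adjusted one as a labelled supportive analysis.
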